9.4.1.4 Interim Visit (Week 8)

Subjects will attend the study site for the Interim (Week 8 ± 4 days) visit, in a fasted state. The subjects will attend the study site from the morning until approximately mid-afternoon.

The proposed chronology of events for the interim procedures and assessments are as follows:

1. Laboratory sampling:
 - A blood sample will be taken for haematology and biochemistry.
 - Urine will be collected. Note: the urine sample can be collected from the subject at any time whilst at the study site, whenever he/she visits the toilet. A urine pregnancy test (WOCBP only) will be performed from this sample at the site.
 - A blood sample will be taken pre-dose for PK analysis (only if the subject can provide the date and time of the last dose of study drug). A second blood sample will be taken 3 to 5 hours post-dose for PK analysis. The exact times of sampling plus the exact time of study drug intake on this day must be documented.

For those subjects who have volunteered for the optional PD sub-study:

- An **optional** blood sample will be taken for PD analysis, i.e. ACTH, DHEAS, androstenedione and testosterone. This sample will be taken from approximately 50 subjects enrolled into the main study, who also volunteer to take part in the sub-study. For optimal results, the sample for androstenedione analysis should be taken between 6 am and 10 am.

2. Register the subject visit using ICON IWRS and dispense study drug.
3. Allow the subject to have breakfast after the laboratory sampling. The subject will take study drug 30 minutes after the start of breakfast and study site staff will document the exact time of study drug intake.
4. Perform physical and neurological examination and vital signs measurement (blood pressure, heart rate, respiration rate, weight and oral temperature). The neurological examination can be conducted \pm 3 days of the scheduled protocol visit. Complete TCNS in the course of the neurological examination, as well as NTSS-6 (with input from the caregiver) to ensure the subject did not develop new signs or symptoms of neuropathy.
5. Review concomitant medications.
6. CSSRS (subject and caregiver).
7. ECG (local ECG equipment with ECG to be read locally by an appropriately qualified and experienced ECG reader at the study site). The same equipment as for Baseline ECG should be used, to avoid errors in calculating QTc.
8. NFM - for details see [Section 12.7](#). Perform the assessment at the area the subject could detect the sensory stimulus during the Week 4 visit. Two measures for each test will be obtained and averaged. Both extremities will be assessed. The test must be undertaken and reviewed by suitably qualified and experienced personnel. The NFM can be conducted \pm 3 days of the scheduled protocol visit. The following tests will be performed:
 - Vibration detection threshold
 - Thermal (cold and warm) detection
 - Nerve conduction (velocity and amplitude)
 - Sensory nerve - Sural nerve or back-up nerves (Ulnar nerve or Median nerve) SNAP and NCV
 - Motor nerve - Peroneal nerve or back-up nerve (Tibial nerve) CMAP and NCV

If any of these NFM tests show a deterioration from the “Before Treatment” status (calculated as the average of the Screening visit and Baseline visit data), please contact ICON MM ([contact]) to define follow-up activities and assess whether the subject must be withdrawn from study.

9. Record AEs. AESIs (worsening of NFM [calculated as the average of the Screening visit and Baseline visit data] or prolongation of QTc) must be treated as SAEs and notified to ICON PV within 24 hours (see [Section 12.1.1](#)). ICON PV or ICON MM will then contact the study site to explain the required next steps for further evaluation.
10. Perform study drug accountability and review Drug Intake Diary for completion compliance.

11. Schedule the EOT (Week 12) visit.
12. Remind the subject to document the time of study drug intake on each day and to attend the EOT (Week 12) visit in a fasted state.
13. Remind the caregiver that he/she is required to be present at all visits (but not for all scales).
14. Before leaving the study site, the second PK sample (3 to 5 hours post-dose; as described in No. 1 above), should be drawn.

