12.1 Adverse Events

12.1.1 Definitions

The definitions for AEs and SAEs are given below. It is of the utmost importance that all staff involved in the study are familiar with the content of this section. The principal investigator is responsible for ensuring this.

Adverse Event

An AE is defined as any untoward medical occurrence in a subject administered a pharmaceutical product, and which does not necessarily have a causal relationship with this treatment. An AE can therefore be any unfavourable and unintended sign, symptom or disease temporally associated with the use of an investigational medicinal product (IMP), whether or not related to the IMP.

Adverse Event of Special Interest

An AESI is an AE of scientific and medical concern specific to the sponsor's product for which ongoing monitoring and rapid communication by the investigator to ICON could be appropriate. Such an event might require further investigation in order to characterize and understand it. These include worsening of NFM qualifying as a potential safety signal (see

[Section 12.7](#)), and prolongation of QTc above the threshold of 480 msec or a change from Baseline > 60 msec. An AESI will be reported similar to an SAE (see below). ICON PV or ICON MM will contact the study site reporting the AESI to discuss the required additional examinations of the affected subject.

Serious Adverse Event

An SAE is defined as, but is not limited to, one that:

- Results in death
- Is life-threatening
- Requires subject hospitalisation or prolongs existing hospitalisation
- Results in persistent or significant disability/incapacity
- Is a congenital anomaly/birth defect
- Is an important medical event*

*Important medical events that may not result in death, be life-threatening or require hospitalisation may be considered a serious adverse drug experience, when based on appropriate medical judgement. They may jeopardise the subject or the subject may require medical or surgical intervention to prevent one of the outcomes listed in this definition. This also includes AESIs.

Where an SAE is reported, a PK sample should be collected, noting both the time at which the last dose of study drug was administered and the time at which the PK sample was collected (see [Section 9.4.1.8](#)).

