12.1.1.3 Reporting of Serious Adverse Events

Investigators and other study site personnel must inform the appropriate ICON representatives of any SAEs and AESIs that occur (whether or not attributable to the study drug) in the course of the study, within 24 hours of when he/she becomes aware of it.

When an SAE or AESI is discovered by the site or is identified by an ICON clinical research associate during site visits, SAEs or AESI will be entered by the site members into the eCRF, which contains specific questions for events regarded as serious. ICON PV will receive the alert through automated e-mail notification.

In case of technical problems in transmitting the SAE through the eCRF within the 24-hour timeline, the investigator/site representative shall complete the SAE form and fax or e-mail to:

For Australia:

[contact]

[contact] (business hours)

[name] (out of hours)

E-mail: [contact]

For the UK:

[contact]

[contact]

E-mail: [contact]

For the USA:

[contact]

[contact]

E-mail: [contact]

If the site staff calls ICON PV to report an SAE, the caller will be prompted to provide the following information, as available:

- Study name, sponsor name, protocol number
- Reporter's name, investigator's name and telephone number
- Site number, subject's study number and subject's initials
- SAE term, start and stop dates of the event
- Relationship to each IMP, action taken in regard to IMP, and subject outcome

The ICON representative will work with the investigator to compile all the necessary information and ensure that the appropriate sponsor representative receives a report within 1 day (24 hours) for all fatal and life-threatening cases and within 5 days for all other SAEs and AESIs.

Follow-up information on SAEs and AESIs must also be reported by the investigator by entering this updated information into the eCRF within the same time frames.

If a non-serious AE becomes serious, this and other relevant follow-up information must also be provided to ICON within 24 hours as described above. The following variables will be recorded for each AE: verbatim/AE description, time and date for AE start and stop, maximum intensity, seriousness, causality rating, whether or not the AE caused the subject to discontinue, and the outcome.

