12.7.1 Reporting Abnormal Nerve Function Monitoring

If the investigator observes any worsening of NFM assessments compared to the subject’s status prior to administration of study drug (subject total Before Treatment status is calculated as the average of the Screening visit and Baseline visit data), they will complete a checklist with a set of additional standard questions that may explain the observation, and inform the ICON MM ([contact]). The subject will continue to receive study drug.

The ICON MM will review the data for this subject within 1 business day and decide whether the event fulfils the criteria of a potential nerve safety signal (i.e. at least two related NFM parameters affected AND no other plausible explanation available). If classified as a potential nerve safety signal, this will be escalated to the DSMB Nerve Function Monitoring sub-committee, as per communication flow and according to timelines detailed in the DSMB Charter. If the event does not fulfil the criteria, the site is informed and the case is closed.

One member of the DSMB Nerve Function Monitoring sub-committee will review the package (in an unblinded fashion) and conclude within two business days whether the finding is:

- a) Confirmed: If Confirmed, the ICON MM is informed and will initiate a stop of dosing of the subject. The case is also escalated to the full DSMB to decide whether the study can progress as planned.
- b) Not confirmed: If Not confirmed, the DSMB Nerve Function Monitoring sub-committee needs to instruct the site, in a blinded manner (via the ICON MM), what additional measures are needed, e.g. to repeat the neurography, include other nerves in the assessment, etc.
- c) Artefact/existing event: If classified as an artefact/existing event, the case is closed and the subject will continue in the study as planned.

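### Five visit steps drop the qualifier from the nerve-function AESI, so a literal reading makes a one-parameter change an SAE that Section 12.7.1 would close

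*Protocol*

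**What the plan says.** Step 9 of the Week 8 visit (Protocol 9.4.1.4) reads "AESIs (worsening of NFM [calculated as the average of the Screening visit and Baseline visit data] or prolongation of QTc) must be treated as SAEs". It requires notice to ICON pharmacovigilance (PV) within 24 hours, cites 12.1.1, and adds "ICON PV or ICON MM will then contact the study site to explain the required next steps for further evaluation". The same parenthesis stands in 9.4.1.3 (step 9), 9.4.1.6 (step 8), 9.4.1.7 (step 7) and 9.4.1.8 (step 5).

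Step 8 of the same Week 8 visit sends the same finding elsewhere: "If any of these NFM tests show a deterioration from the" pre-treatment status, the site is to contact the Medical Monitor.

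Section 12.1.1 defines the two AESIs more tightly. For nerve function: "These include worsening of NFM qualifying as a potential safety signal", with a reference to 12.7. For the ECG: "prolongation of QTc above the threshold of 480 msec or a change from Baseline > 60 msec". Its SAE definition, in the note on important medical events, says "This also includes AESIs". Section 12.1.1.3 sets the reporting clock for SAEs and AESIs: "within 24 hours of when he/she becomes aware of it".

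Section 12.7.1 covers any worsening against the Screening/Baseline average. Of investigators it says "they will complete a checklist with a set of additional standard questions that may explain the observation, and inform the ICON MM"; dosing continues. The Medical Monitor then has one business day to decide whether the event is a potential nerve safety signal, meaning that two or more related parameters are affected and nothing else plausibly explains it. If not, the site is told and the case ends. If so, the case goes to the DSMB Nerve Function Monitoring sub-committee, with communication flow and timelines left to the DSMB Charter.

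SAP 7.8.1 tabulates treatment-emergent AESIs and serious TEAEs. It adds no nerve criterion of its own.

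**The concern.** The visit sections are what site staff work from on the day. There the nerve AESI is any worsening from the pre-treatment average. In the definition and in 12.7.1 it is worsening that has passed a two-parameter test applied by the Medical Monitor. The two rules give different answers for the same patient whenever a single parameter worsens, or when several worsen for a known reason.

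Because 12.1.1 places AESIs among SAEs, the difference carries through. An SAE brings a PK sample (12.1.1, 9.4.1.8), ethics committee notice as local rules require (12.1.1.3), and an entry in both SAP tables. One site could file an SAE where another sends a checklist and sees the case closed. NFM is a dedicated safety objective of this trial, so its AESI count should mean the same thing at every site.

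**Working it through.** **The plan's one NFM figure.** Protocol 15.1 states the chance of seeing at least one event in an arm of 78. At a true rate of 3%: 1 − 0.97^78 = 0.907 (stated as approximately 90%). At 5%: 1 − 0.95^78 = 0.982 (stated as > 98%). Both reproduce, and neither depends on how an AESI is defined. The rest is a comparison of text.

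**The five visit sections side by side.**

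| Visit | AESI step | Two-parameter test stated? | Separate Medical Monitor step for deterioration? | Time limit on that contact |
|---|---|---|---|---|
| Week 4 (9.4.1.3) | 9 | No | Yes, step 8 | None |
| Week 8 (9.4.1.4) | 9 | No | Yes, step 8 | None |
| EOT (9.4.1.6) | 8 | No | Yes, step 4 | None |
| Follow-up (9.4.1.7) | 7 | No | Yes, step 3 | None |
| Unscheduled (9.4.1.8) | 5 | No | No | Not applicable |

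So 0 of 5 state the test, 4 of 5 have a Medical Monitor contact step, and 0 of those 4 put a time on it. Baseline (9.4.1.2, step 7) does: 24 hours from awareness.

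**One case under both rules.** Suppose that at Week 8 one conduction velocity is below the Screening/Baseline average and everything else is unchanged.

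1. Step 9 read literally: NFM has worsened, so it is an AESI, treated as an SAE and notified to PV within 24 hours.
2. Section 12.7.1: checklist and Medical Monitor. One parameter is fewer than two, so the case is closed. It is not an AESI under 12.1.1.

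**Is the parenthesis only a label?** It also shortens the ECG criterion, which favours shorthand. Two features point the other way. First, it carries a comparison rule, the Screening/Baseline average, and 12.7.1 uses that same comparator for any worsening, the trigger for the checklist. Second, the order differs: the visit step puts PV notice first and contact with the site afterwards, while 12.7.1 puts classification first. A site can apply 480 msec or 60 msec itself. Under 12.7.1 it cannot make the nerve decision.

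**Does 12.7.1 tell the site that an event qualified?** At classification, the one notice to the site that is written down concerns events that do not qualify. After escalation:

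- Confirmed: the Medical Monitor initiates a dosing stop, which implies site contact.
- Not confirmed: the site is instructed through the Medical Monitor on further measures.
- Artefact or existing event: the case is closed and the subject continues.

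None of these says, at classification, that the site now holds an AESI. The Charter, which was not supplied, may say so.

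**Size.** A count would need a cut-off for worsening and the share of sites that read the step literally. The documents give neither.

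**The case against.** The strongest reply is that nothing conflicts. Each step cites 12.1.1, where the definition sits, and trims QTc in the same way. In four of the five visits a separate NFM step, placed before the AE step, already sends any deterioration to the Medical Monitor. Reporting first and evaluating second is also a defensible conservative order for an event of special interest. Much of this stands: shorthand is a fair reading, and the point is an ambiguity to be cleared up. It does not settle the matter, because the steps impose SAE handling on wording that matches the checklist trigger and not the definition.

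Several stronger readings are tempting, and the documents do not support them.

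- A reader might infer that 12.7.1 tells the site nothing once an event qualifies. It does not say that. One branch instructs the site, another implies contact, 12.1.1 provides for contact with a site that reports an AESI, and the communication flow sits in the Charter.
- A reader might take 12.1.1 itself to require the Medical Monitor's classification. It does not name the Medical Monitor; that comes through its reference to 12.7.
- A reader might see the unscheduled visit as leaving the site alone. That visit is prompted by an SAE that is already reportable, Table 1 schedules no full NFM there, and its last step provides for PV or Medical Monitor contact.
- A reader might infer bias between arms. Randomisation is blocked within site and investigators are blinded (10.2.4), so a site's habit would be expected to fall on both arms.

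**Conclusion.** The point holds as a wording inconsistency with a limited reach. Five visit steps state the nerve AESI without the qualifier that 12.1.1 applies and 12.7.1 defines, and read literally they turn non-qualifying changes into SAEs. What could vary by site is the AESI and serious TEAE counts in SAP 7.8.1. No inflation factor can be given. Dosing stops and sub-committee or DSMB review follow 12.7.1, and the NFM summaries use the measurements themselves, so none of these is shown to change; nor is the comparison between arms.

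A second, smaller gap is that 12.7.1 has no explicit step telling the site, at classification, that its event qualified. The conclusion assumes that some sites would follow the visit step as written and that the unseen Charter does not already settle site notice. It is worth correcting because the correction is nearly free, not because a result is at risk.

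**What to change.** 1. In 9.4.1.3, 9.4.1.4, 9.4.1.6, 9.4.1.7 and 9.4.1.8, replace *worsening of NFM* with *worsening of NFM qualifying as a potential nerve safety signal per Section 12.7.1*.
2. In 12.1.1, change the cross-reference from 12.7 to 12.7.1.
3. In 12.7.1, require contact with the Medical Monitor within 24 hours of awareness of any worsening, the limit that Baseline step 7 already uses.
4. In 12.7.1, state that the Medical Monitor tells the site when an event is classified as a signal, and that PV is notified promptly at that point.
5. State that events serious on other grounds keep the 24-hour rule.

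The SAP needs no change, and there are no new data, visits or tables. The costs are re-briefing sites and somewhat later formal PV notice for true signals. Classification would come at most 24 hours plus one business day after awareness: Monday awareness gives Tuesday, then Wednesday (2 days); Thursday gives Friday, then Monday (4 days); Friday gives Saturday, then Monday (3 days). A public holiday would add to this. PV notice follows, against 24 hours from awareness under the literal visit step. The Medical Monitor would know of the worsening within 24 hours in every case.

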9.4.1.5 Telephone Contact (Ad Hoc)

Subjects can telephone the study sites at any time during the study in order to report an AE. At this contact, site staff will be required to:

1. Question the subject about any new/updates on AEs.
2. Question the subject to determine any changes to concomitant medications.
3. Complete NTSS-6 (with input from the caregiver) to ensure the subject did not develop new signs or symptoms of neuropathy.
4. Remind the subject of the date of next visit, if applicable.
5. Remind the subject to document the exact time of study drug intake each day.
6. Remind the caregiver that he/she is required to be present at all visits (but not for all scales).

9.4.1.6 End of Treatment Visit (Week 12)

Subjects will attend the study site for the EOT (Week 12 \pm 4 days) visit, in a fasted state. The subjects will attend the study site from the morning until approximately mid-afternoon. This is also an early termination visit for subjects who withdraw prior to Week 12.

Proposed chronology of events for the EOT procedures and assessments are as follows:

1. Laboratory sampling:
 - A blood sample will be taken for haematology and biochemistry, including metabolic function testing (HbA1c, glucose and lipids).
 - Urine will be collected. Note: the urine sample can be collected from the subject at any time whilst at the study site, whenever he/she visits the toilet. A urine pregnancy test (WOCBP only) will be performed from this sample at the site.
 - A blood sample will be taken for PK analysis (only if the subject can provide the date and time of the last dose of study drug). The exact time of sampling must be documented.

For those subjects who have volunteered for the optional PD sub-study:

- An **optional** blood sample will be taken for PD analysis, i.e. ACTH, DHEAS, androstenedione and testosterone for PD analysis. This sample will be taken from approximately 50 subjects enrolled into the main study, who also volunteer to take

part in the sub-study. For optimal results, the sample for androstenedione analysis should be taken between 6 am and 10 am.

2. Allow the subject to have breakfast after the laboratory sampling.
3. Perform physical and neurological examination and vital signs measurement (blood pressure, heart rate, respiration rate, weight and oral temperature). The neurological examination can be conducted \pm 3 days of the scheduled protocol visit. Complete TCNS in the course of the neurological examination, as well as NTSS-6 (with input from the caregiver) to ensure the subject did not develop new signs or symptoms of neuropathy.
4. NFM - for details see [Section 12.7](#). Perform the assessment at the area the subject could detect the sensory stimulus during the Week 8 visit. Two measures for each test will be obtained and averaged. Both extremities will be assessed. The test must be undertaken and reviewed by suitably qualified and experienced personnel. The NFM can be conducted \pm 3 days of the scheduled protocol visit. The following tests will be performed:
 - Vibration detection threshold
 - Thermal (cold and warm) detection
 - Nerve conduction (velocity and amplitude)
 - Sensory nerve - Sural nerve or back-up nerves (Ulnar nerve or Median nerve) SNAP and NCV
 - Motor nerve - Peroneal nerve or back-up nerve (Tibial nerve) CMAP and NCV

If any of these tests show a deterioration from the “Before Treatment” status (calculated as the average of the Screening visit and Baseline visit data), please contact ICON MM ([contact]) to define the follow-up activities and assess whether the subject must be withdrawn from study.

5. Review concomitant medications.
6. Neuropsychological scales (ADAS-Cog v14 [subject only], CDR-SOB [subject and caregiver], MMSE [subject only], RAVLT [subject only], NTB [subject only], NPI [caregiver only] and CSSRS [subject and caregiver]):
 - The neuropsychological testing should be performed during the same period of the day at the Screening, Baseline (Week 0) and EOT (Week 12) visits to minimise a confounding impact of fluctuations in vigilance
7. ECG (local ECG equipment with ECG to be read locally by an appropriately qualified and experienced ECG reader at study site). The same equipment as for Baseline ECG should be used, to avoid errors in calculating QTc.
8. Record AEs. AESIs (worsening of NFM [calculated as the average of the Screening visit and Baseline visit data] or prolongation of QTc) must be treated as SAEs and notified to

ICON PV within 24 hours (see [Section 12.1.1](#)). ICON PV or ICON MM will then contact the study site to explain the required next steps for further evaluation.

9. Perform study drug accountability and review Drug Intake Diary for completion compliance.

9.4.1.7 Follow-up Visit (4 Weeks Post Last Dose of Study Drug \pm 4 Days)

Subjects who complete the 12-week double-blind treatment period, or subjects who terminated early, will attend a Follow-up (4 weeks post last dose of study drug \pm 4 days) visit for safety purposes, in a fasted state. The subjects will spend the morning at the study site.

Follow-up procedures and assessments are as follows:

1. Laboratory sampling:

- A blood sample will be taken for haematology and biochemistry.
- Urine will be collected. Note: the urine sample can be collected from the subject at any time whilst at the study site, whenever he/she visits the toilet. A urine pregnancy test (WOCBP only) will be performed from this sample at the site.

For those subjects who have volunteered for the optional PD sub-study:

- An **optional** blood sample will be taken for PD analysis, i.e. ACTH, DHEAS, androstenedione and testosterone. This sample will be taken from approximately 50 subjects enrolled into the main study, who also volunteer to take part in the sub-study. For optimal results, the sample for androstenedione analysis should be taken between 6 am and 10 am.
2. Perform physical and neurological examination and vital signs measurement (blood pressure, heart rate, respiration rate, weight and oral temperature). The neurological examination can be conducted \pm 3days of the scheduled protocol visit. Complete TCNS in the course of the neurological examination, as well as NTSS-6 (with input from the caregiver) to ensure the subject did not develop new signs or symptoms of neuropathy.
 3. NFM - for details see [Section 12.7](#). Perform the assessment at the area the subject could detect the sensory stimulus during the Week 12 visit. Two measures for each test will be obtained and averaged. Both extremities will be assessed. The test must be undertaken and reviewed by suitably qualified and experienced personnel. The NFM can be conducted \pm 3 days of the scheduled protocol visit. The following tests will be performed:
 - Vibration detection threshold
 - Thermal (cold and warm) detection
 - Nerve conduction (velocity and amplitude)
 - Sensory nerve - Sural nerve or back-up nerves (Ulnar nerve or Median nerve) SNAP and NCV

- Motor nerve - Peroneal nerve or back-up nerve (Tibial nerve) CMAP and NCV

If any of these tests show a deterioration from the “Before Treatment” status (calculated as the average of the Screening visit and Baseline visit data), please contact ICON MM ([contact]) to define the follow-up activities.

4. Review concomitant medications.
5. Complete the CSSRS (subject and caregiver).
6. ECG (local ECG equipment with ECG to be read locally by an appropriately qualified and experienced ECG reader at the study site). The same equipment as for Baseline ECG should be used, to avoid errors in calculating QTc.
7. Record AEs. AESIs (worsening of NFM [calculated as the average of the Screening visit and Baseline visit data] or prolongation of QTc) must be treated as SAEs and notified to ICON PV within 24 hours (see [Section 12.1.1](#)). ICON PV or ICON MM will then contact the study site to define follow-up activities and to assess whether the subject must be withdrawn from study.

